5.5. Study Procedures

Subjects are considered enrolled at the time the study-specific ICF is signed. Each subject must meet all of the inclusion criteria and no exclusion criteria to be eligible to continue participation in this study. Following qualification using a 3-day baseline urinary voiding diary, MESA urinary incontinence questionnaire and pregnancy test (if applicable), subjects will undergo 12 PTNM therapy sessions, administered weekly (\pm 3 days), utilizing the NURO system. Urinary voiding diaries (3-day) to assess efficacy measures and quality of life questionnaires will be completed as indicated in Figure 1-1: Study Procedures. The study is expected to last approximately 14 weeks per subject following the enrollment visit. Subjects will be exited from the study after the final study visit is complete.

Figure 1-1: Study Procedures

6. Determination of Sample Size

This study is designed to evaluate the reduction from baseline in the number of UUI episodes per day after the 12th PTNM therapy session. The OrBIT trial by Peters et al (2009)¹ compared the effectiveness of PTNS to extended-release tolterodine. This study reported an average reduction of UUI at 12 weeks compared to baseline in the PTNS arm was 1 episode per day with a standard deviation of 2.2. The following assumptions were used for the sample size calculations: reduction of 0.75 UUI episodes/day from baseline, one-sample t-test with two-sided $\alpha=0.05$, 90% power, and an estimated standard deviation of 2.2 incontinence episodes/day. Based on these assumptions, a sample size of 93 subjects would be required to demonstrate a statistically significant reduction from baseline. To account for an

attrition of approximately 20% during the study, a sample size of up to 120 subjects is required for this study.

The sample size requirement of 93 for the primary objective is also adequate to assess the secondary objectives of number of voids per day and quality of life measured by OABq. In the OrBIT trial by Peters et al (2009)¹, the average reduction of voids at 12 weeks compared to baseline in the PTNS arm was 2.4 voids per day with a standard deviation of 4.0. Based on a one-sample t-test, with $\alpha=0.05$ two-sided, 90% power, 44 subjects with urgency frequency (UF) are required to demonstrate a statistically significant reduction from baseline if using a conservative estimate of a reduction of 2.0 voids per day with a standard deviation of 4.0. In the InSite study, among all implanted subjects 63% of the urinary incontinence (UI) subjects had both UI and UF at baseline. Therefore, 93 subjects should ensure the sample size needed for the secondary objective of UF based on this assumption.

In the OrBIT trial by Peters et al (2009)¹, the average improvement from baseline of HRQL from OABq for PTNS at 12 weeks was 25.3 ± 21.5 . Based on a one-sample t-test, with $\alpha=0.05$ two-sided, 90% power, 15 subjects are required to demonstrate a statistically significant reduction from baseline when using a conservative estimate of average improvement of 20 points at 12 weeks with a standard deviation of 22. Therefore, 93 subjects should ensure the sample size needed for the secondary objective of OABq.

7. Statistical Methods

7.1. Study Subjects

7.1.1. Disposition of Subjects

Subject disposition will be summarized by study visit in a flow diagram. Discontinuation will be summarized by visit and discontinuation reasons will be provided.

7.1.2. Clinical Investigation Plan (CIP) Deviations

CIP deviations occurring during the study will be summarized by deviation type.

7.1.3. Analysis Sets

Throughout the document, all qualified subjects refer to subjects who meet inclusion/exclusion criteria.

Subjects used for analyses are described in each objective under Section 7.9.

7.2. General Methodology

The analysis methods are provided under each subsection in Section 7.9. In all analyses when p-value is calculated, a statistical test is deemed significant if the P value is less than 0.05.

7.3. Center Pooling

Data from all study centers will be pooled for the analysis. There are no planned statistical methods to test for treatment differences among centers. The study will be conducted at approximately 15 sites in

the US. Initial site enrollment is not planned to exceed 20% of the total number of subjects that are qualified for the study; however, this may be increased based on the Sponsor's discretion. This is intended to reduce the possibility that a site with atypical results will be overly influential in the overall study results.

7.4. Handling of Missing, Unused, and Spurious Data and Dropouts

For the primary objective and secondary objectives, primary analysis method will be based on the completers dataset, with no imputation of missing data. Sensitivity analyses with various missing data handling approaches will be conducted as described in Section 7.9.1. Secondary objectives will be analyzed in a similar matter as detailed in Section 7.9.2.

7.5. Adjustments for Multiple Comparisons

This is a single arm study, with a primary objective to evaluate the efficacy of PTNM on UUI episodes per day at the 12th PTNM session from baseline. No adjustments for multiple comparisons were made in this study.

7.6. Demographic and Other Baseline Characteristics

Demographics and other baseline characteristics will be summarized for subjects who are qualified for the study and receive PTNM treatment including:

- Age, gender, race and ethnicity
- Diagnosis, years since diagnosis
- Body Mass Index (BMI)
- Medical history
- Surgery history
- Conservative therapies for OAB
- Baseline UUI episodes per day, baseline voids per day (for UF subjects only), average degree of urgency, average nighttime voiding frequency and nocturia.

7.7. Treatment Characteristics

Motor and sensory response during therapy sessions will be summarized by PTNM session. If multiple sessions are used to complete a session visit, the motor and sensory response values from the last session in that visit will be used for summary.

During the study, if a subject starts an OAB medication following the first PTNM therapy session, a deviation form will be completed and the medication will be captured on the OAB medication form.

7.8. Interim Analyses

No interim analysis was planned for this study.

7.9. Evaluation of Objectives

7.9.1. Primary objective

This study will assess the efficacy of PTNM on UUI episodes collected using a voiding diary. The primary objective is to demonstrate a statistically significant reduction between baseline and following the 12th PTNM therapy session in the number of UUI episodes per day.

Hypothesis

$H_0: \mu_{12\text{th PTNM therapy session}} = \mu_{\text{baseline}}$

$H_a: \mu_{12\text{th PTNM therapy session}} \neq \mu_{\text{baseline}}$

Where μ_{baseline} and $\mu_{12\text{th PTNM therapy session}}$ are average UUI episodes per day at baseline and following the 12th PTNM therapy session respectively.

Endpoint definition

The average UUI episodes per day collected at baseline and following the 12th and final PTNM therapy session will be used as the endpoint for the primary objective. Average UUI episodes per day will be calculated by summing all reported leaks and dividing by the total number of days of diaries.

For a diary to be included in the analysis, it needs to have complete leak and/or void episode entries for at least one day. For any reported episode if leak or void is not indicated, the diary of that day will not be included.

Data collection and analysis methods

Diary data collected at baseline and after the 12th PTNM therapy session will be used for the primary endpoint analysis. Reduction in average UUI episodes per day from baseline will be calculated for each subject after the 12th PTNM. The paired t-test or the Wilcoxon signed-rank test will be used to evaluate the changes after testing for data normality by calculating Shapiro-Wilk W statistic. A statistical test is deemed significant if the P value is less than 0.05. Primary analysis method will be completers (with no imputation of missing data). Sensitivity analyses will be conducted with the adjusted worst-case method and per protocol analysis.

Determination of subjects for analysis

Qualified subjects with diary data from both baseline and the 12th PTNM therapy session will be included in the primary analysis for this objective.

In addition to the primary analysis, two sensitivity analyses will be performed:

- Adjusted worst-case analysis, in which,
 - a. For subjects who received the study therapy and withdrew early due to device or therapy/procedure -related adverse events, or treatment unsuccessful, the 12th PTNM therapy session data point will be set to subject's baseline assessment.
 - b. For subjects who received the study therapy and exit the study early due to all other reasons (i.e. adverse events not related to the device or therapy), and for subjects who missed the 12th PTNM therapy session or fail to provide the relevant data for 12th PTNM therapy session, the Last Observation Carried Forward (LOCF) method will be used to impute the missing data.
 - c. Subjects who exit the study prior to the initial NURO PTNM therapy session will be excluded from this sensitivity analysis
- Per protocol sensitivity analysis which will be based on the completers dataset, but will exclude those subjects who take OAB medications in the study. Use of OAB medications will be captured as a protocol deviation.

Besides PTNM session 12, diary data are also collected for PTNM Session #1, #4, and #8. Reduction in number of UUI episodes from baseline will be summarized for each follow up visit (PTNM session #1, #4, #8 and #12) when the diary data is collected with no imputation of missing data (completers analysis).

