	
relevant medical history. The MESA urinary incontinence questionnaire will be used to exclude predominant stress incontinence. If the Investigator's assessment differs from the results of the MESA questionnaire, rationale must be documented to explain the decision to enroll the subject.
 
Subjects will complete the following required questionnaires: OABq, UPS, PPBC, and SAGA at the enrollment/baseline visit. The 3-day urinary baseline voiding diary, pregnancy test (if of childbearing potential) must be completed prior to the initial therapy session. For subjects who have dual incontinence (defined as bladder and fecal incontinence), a 7-day fecal incontinence diary will be recommended at baseline in addition to the 3-day urinary voiding diary.
 
Weekly PTNM Therapy Session Visits (PTNM Sessions #1-#12)
 
At the weekly follow-up visits, OAB medication(s) and adverse events will be collected from the subject. Following completion of all visit-specific data collection, subjects will then complete a NURO therapy session in accordance with the NURO System Instructions for Use.
 
Approximately one day after PTNM therapy sessions #1, #4, #8 and #12, subjects will start their 3-day urinary voiding diary. OABq, UPS, and PPBC questionnaires will be completed prior to starting PTNM therapy sessions #2, #5 and #9. Questionnaires must be completed prior to the therapy session. Following completion of all visit-specific data collection, subjects will then complete a NURO therapy session.
 
Final Study Visit
 
At the final study visit, the subject's 3-day urinary voiding diary will be collected. For subjects who have dual incontinence, a 7-day fecal incontinence diary will be recommended in addition to the 3-day urinary voiding diary. Any OAB medication(s) and adverse events will be collected from the subject. Subjects will complete the required questionnaires associated with the OABq, UPS, PPBC, SAGA and PGI-I. Subjects will then be exited from study.

Safety Assessments	Safety will be evaluated by the collection of reportable adverse events.
Statistics	The sample size estimate is based on a one-sample t-test, with $\alpha=0.05$ two-sided, 90% power and an estimated standard deviation of 2.2 UUI episodes/day. If the mean reduction in number of UUI episodes is expected to be .75 per day after 12 PTNM therapy sessions compared to baseline, a sample size of 93 subjects would be required to demonstrate

Confidential

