9.4. Exclusion Criteria

A potential subject who meets any of the following criteria will be excluded from participating in the study:

1. Have received anticholinergics/antimuscarinics or beta 3-agonists medications to treat OAB or advanced therapy treatment options for OAB (botulinum toxin injections, sacral neuromodulation, or percutaneous tibial nerve stimulation/neuromodulation)
2. Primary stress incontinence or mixed incontinence where the stress component overrides the urge component (see enrollment/baseline requirements for use of the MESA urinary incontinence questionnaire)
3. Have implantable pacemakers or implantable defibrillators

Confidential

4. Use of transcutaneous electrical nerve stimulation (TENS) in pelvic region, back or legs
5. Women who are pregnant or planning to become pregnant during the course of the study (women of child-bearing potential must undergo a pregnancy test, with a clear negative result, prior to first PTNM session)
6. Characteristics indicating a poor understanding of the study or characteristics that indicate the subject may have poor compliance with the study protocol
7. Nerve damage that could impact either tibial nerve or pelvic floor function.
8. Subjects prone to excessive bleeding
9. Inadequate skin integrity in the area of PTNM needle placement
10. History of diabetes unless the diabetes is well-controlled through diet and/or medications
11. Have symptomatic urinary tract infection (UTI)
12. Participation in any research study involving or impacting gynecologic, urinary or renal function within the 4-week period prior to or plans to participate during study enrollment

10. Study Procedures

The study schedule, procedures, and methods of assessment are defined in detail to enable compliance with the required activities, and to ensure that the resulting data meet the criteria for evaluability. See Table 1-1 for visit requirements. Both paper and electronic case report form (eCRF) will be provided for use in collecting data for all subjects; the pertinent eCRFs along with the applicable source documentation will be completed for each subject.

Enrollment/Baseline

Subjects are considered enrolled at the time the study-specific ICF is signed. Each subject must meet all of the inclusion criteria and no exclusion criteria to be eligible to continue participation in this study.

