5.4. Exclusion Criteria

A potential subject who meets any of the following criteria will be excluded from participating in the study:

[figure not shown]
1. Have received anticholinergics/antimuscarinics or beta 3-agonists medications to treat OAB or advanced therapy treatment options for OAB (botulinum toxin injections, sacral neuromodulation, or percutaneous tibial nerve stimulation/neuromodulation)
2. Primary stress incontinence or mixed incontinence where the stress component overrides the urge component (see enrollment/baseline requirements for use of the MESA urinary incontinence questionnaire)
3. Have implantable pacemakers or implantable defibrillators
4. Use of transcutaneous electrical nerve stimulation (TENS) in pelvic region, back or legs
5. Women who are pregnant or planning to become pregnant during the course of the study (women of child-bearing potential must undergo a pregnancy test, with a clear negative result, prior to first PTNM session)
6. Characteristics indicating a poor understanding of the study or characteristics that indicate the subject may have poor compliance with the study protocol
7. Nerve damage that could impact either tibial nerve or pelvic floor function.
8. Subjects prone to excessive bleeding
9. Inadequate skin integrity in the area of PTNM needle placement
10. History of diabetes unless the diabetes is well-controlled through diet and/or medications
11. Have symptomatic urinary tract infection (UTI)

12. Participation in any research study involving or impacting gynecologic, urinary or renal function within the 4-week period prior to or plans to participate during study enrollment

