7.9.3.3. Urgency including the Urgency Perception Scale (UPS)

Objective:

To summarize UPS at baseline and by PTNM sessions for subjects who receive PTNM therapy.

Endpoint definition:

UPS is a three-category scale to measure the urgency perceptions based on subjects' experience when they have a desire to urinate.

Data collection and analysis methods:

UPS data are collected for baseline and the 1st, 4th, 8th and 12th PTNM sessions. Number of subjects and percent of subjects in each category of the scale will be summarized by visit.

As an additional analysis to look at urgency besides UPS, urgency is also collected for diary episodes such as no urgency, mild, moderate and severe. The following scores will be assigned to each urgency degree: 0= no urgency; 1=mild; 2=moderate; 3=severe. Average urgency score will be calculated by summing urgency scores for leaking episodes and dividing by the total number of leaks in 3-day voiding diary when urgency is reported. Average urgency score will be reported at baseline and 1st, 4th, 8th and 12th PTNM sessions. For a diary to be included in the analysis, it needs to have complete leak and/or void episode entries for at least one day. For any reported episode if leak or void is not indicated, the diary of that day will not be included.

Determination of subjects for analysis:

All qualified subjects who receive PTNM therapy and have data available will be included in the analysis.

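### The primary endpoint is named UUI episodes per day, but SAP 7.9.1 counts every leak, and no planned analysis counts leaks with urgency

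*SAP*

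**What the plan says.** SAP 7.9.1 names the primary endpoint as average UUI episodes per day at baseline and after the 12th session, then gives one counting rule: "Average UUI episodes per day will be calculated by summing all reported leaks and dividing by the total number of days of diaries". The only other diary rules there concern completeness. A diary needs at least one complete day, and "For any reported episode if leak or void is not indicated, the diary of that day will not be included". Protocol 14.3 uses the same endpoint name and gives no counting rule.

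SAP 7.9.3.3 states that "urgency is also collected for diary episodes such as no urgency, mild, moderate and severe". It scores these grades from 0 (none) to 3 (severe) and obtains an average by "summing urgency scores for leaking episodes and dividing by the total number of leaks in 3-day voiding diary when urgency is reported".

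For eligibility, Protocol section 10 (initial therapy session) and Protocol 10.10 require at least three UUI episodes with mild, moderate or severe urgency on the three-day diary. Mixed incontinence is a reason for exclusion only where stress predominates: "Primary stress incontinence or mixed incontinence where the stress component overrides the urge component" (SAP 5.4; Protocol 9.4 has the same criterion).

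The primary result has two sensitivity analyses. The adjusted worst-case analysis changes how missing data are filled in. The per-protocol analysis is "based on the completers dataset, but will exclude those subjects who take OAB medications in the study".

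**The concern.** The name and the rule describe different quantities. UUI is leakage with urgency, while the rule counts leakage of any kind. The data that separate the two are collected, and the protocol makes the separation when it decides who qualifies, but the endpoint rule does not use it.

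If an enrolled subject records a leak without urgency, it enters the primary endpoint as UUI. The primary test, both sensitivity analyses and the by-visit summaries would then report a change in all leaks under the name UUI. A reader of the final report could not tell how much of the change was urge leakage, which is the study's stated primary question.

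**Working it through.** **1. Can a leak without urgency enter the count?**

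- SAP 7.9.1 sets no urgency condition, and Protocol 14.3 supplies none.
- SAP 7.9.3.3 applies a scale with a zero level to leaking episodes, so the scoring has a place for such a leak.
- The exclusion removes "mixed incontinence where the stress component overrides the urge component" (Protocol 9.4), so urge-predominant mixed incontinence can be enrolled. The MESA questionnaire screens for stress predominance, but the investigator may enroll against it with a documented rationale (Protocol section 10 and 10.2).
- By the eligibility wording in Protocol section 10 and 10.10, a leak with no urgency would not help a subject qualify. By SAP 7.9.1 the same leak would count toward the endpoint.

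**2. Does any planned output give the count of leaks with urgency?**

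- Adjusted worst-case: same count, different imputation.
- Per-protocol: same count, fewer subjects.
- By-visit summaries (SAP 7.9.1): same count.
- UPS: a three-category questionnaire, not a diary count.
- Diary urgency: Protocol 14.5 promises reductions in urgency by session, which the SAP carries out as a mean score per graded leak. With mean score m between 1 and 3, the share of graded leaks scored 0 can lie anywhere from 0 to 1 − m/3, the maximum arising when all other leaks score 3. For m = 1.5 that is 0–50%; for m = 2.0, 0–33%; for m = 2.5, 0–17%. This bounds the share of leaks if scores are pooled over leaks. If scores are averaged within subject first, it bounds the average subject's share instead. The score is also undefined for a subject with no graded leak, such as one who is dry after session 12.

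**3. How much would it take to change the test result?**

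Inputs (Protocol 14.1.1 and SAP 6): fall 0.75/day, SD 2.2, two-sided alpha 0.05, 90% power, n = 93. The same sections quote a fall of 1.0/day from an earlier trial. With 120 subjects and 20% attrition, n = 120 × 0.80 = 96.

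The plan's figure reproduces. The normal approximation gives ((1.960 + 1.282) × 2.2 / 0.75)² = 90.4, so 91. The exact one-sample t-test gives 93, with power 90.2%.

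Smallest significant mean fall = t(0.975, n − 1) × 2.2 / √n:

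- n = 93: 1.9861 × 2.2 / √93 = 0.453/day
- n = 96: 1.9853 × 2.2 / √96 = 0.446/day

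Part of the all-leak fall that non-urge leaks must supply before the urge-only fall loses significance, with SD 2.2 also assumed for urge-only leaks:

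| All-leak fall | n = 93 | n = 96 |
|---|---|---|
| 0.75/day | 0.75 − 0.453 = 0.297 (40%) | 0.75 − 0.446 = 0.304 (41%) |
| 1.0/day | 1.0 − 0.453 = 0.547 (55%) | 1.0 − 0.446 = 0.554 (55%) |

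These thresholds are for the t-test. They do not carry over if the normality check leads to the Wilcoxon test.

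**4. What could happen to the estimate?**

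An assumed share shows the effect: if 20% of a 0.75/day fall lay in non-urge leaks, the urge-leak fall would be 0.75 × 0.80 = 0.60/day. If non-urge leaks instead did not change on average, the mean fall would be the same under both counts and only variance would be added. Assuming an independent non-urge change with SD 0.5, 1.0 or 1.5, the all-leak SD is √(2.2² + s²) = 2.26, 2.42 or 2.66, and power at n = 93 is 88.7%, 84.2% or 76.7%. The documents do not say which case applies.

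**The case against.** The strongest reply is that leak is shorthand for the UUI entry on the diary. SAP 7.9.1 and Protocol 10.6 both speak of the diary as the source of UUI episodes, the MESA screen removes predominant stress incontinence, and the eligibility wording in Protocol section 10 secures at least three urge leaks in three days at baseline. The zero grade belongs to a scale for diary episodes in general, voids included, so its existence does not show that leaks without urgency are expected.

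Much of this stands. The documents do not show that non-urge leaks are common, or that the two counts will differ materially. But the shorthand is nowhere stated, the rule refers to all reported leaks, and the urgency scale is applied to leaks without removing the zero level. If the diary form does limit leak entries to urge leaks, one sentence in 7.9.1 would settle it.

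A reader might infer that the sample size rests on a different endpoint, because the Protocol synopsis gives "an estimated standard deviation of 2.2 UUI episodes/day" while Protocol 14.1.1 and SAP 6 attach the same SD to incontinence episodes. That does not follow. Those two sections use both terms within one sentence, which is loose wording and no separate evidence.

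**Conclusion.** The point holds as a mismatch between the endpoint's name and its counting rule, with no planned output that closes the gap. It should be fixed, and it affects mainly the meaning of the estimate.

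A reader might go further and infer that the primary result will overstate the UUI benefit, or that its significance is unsafe. The documents support neither. The frequency of non-urge leaks and the direction of any effect are unknown. With the plan's t-test inputs and SD 2.2 assumed for both counts, non-urge leaks would have to supply about 40% of a 0.75/day fall, or 55% of a 1.0/day fall, to remove significance. The sample size of 93 is not in question.

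**What to change.** Keep the all-leak count as the primary analysis, and make these changes:

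1. State in SAP 7.9.1 that the endpoint counts all reported leaks, and word the conclusion accordingly. Reconcile this with the UUI wording in the Protocol synopsis, Protocol 6.2.1 and 14.3, and SAP 4.1, and record it in SAP 7.11, which now reports no changes. Editing 7.9.1 alone would create a new conflict.
2. Add a prespecified sensitivity analysis that counts only leaks graded mild, moderate or severe per valid diary day, in the same completers set, with the same test, after session 12.
3. Give a rule for ungraded leaks: one run counting them as urge leaks and one run not. The valid-day rule drops a day for a missing leak or void entry but does not address a missing urgency grade.
4. Tabulate the share of leaks graded as without urgency, and the share ungraded, at baseline and after session 12.

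The cost is wording in both documents, one sensitivity analysis run twice and one table, all from data already collected. Sample size, diary and visits do not change. The drawback is that the graded count depends on a subjective grade that may shift in an open-label study, so it should be supportive and not primary.

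### Must one primary test be fixed in advance, given that a normality pre-test can move the primary p-value from the paired t-test to Wilcoxon?

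*SAP*

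**What the plan says.** SAP 7.9.1 and protocol 14.3 set the null as equality of two μ values, which "are average UUI episodes per day at baseline and following the 12th PTNM therapy session respectively". For the test, SAP 7.9.1 says: "The paired t-test or the Wilcoxon signed-rank test will be used to evaluate the changes after testing for data normality". Protocol 14.3 has the same rule but names no normality test. The SAP names one: "after testing for data normality by calculating Shapiro-Wilk W statistic". Neither document says outright which result leads to which test. The only available threshold is the general one in SAP 7.2: "In all analyses when p-value is calculated, a statistical test is deemed significant if the P value is less than 0.05".

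SAP Section 6 bases the sample size on a "reduction of 0.75 UUI episodes/day from baseline, one-sample t-test with two-sided" alpha of 0.05, with 90% power and an SD of 2.2, which gives 93. The effect is set below that of a cited randomised trial, whose mean UUI reduction "in the PTNS arm was 1 episode per day with a standard deviation of 2.2".

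SAP 7.9.1 adds: "In addition to the primary analysis, two sensitivity analyses will be performed". These are the adjusted worst-case and per-protocol analyses. They change the imputation or the subjects, not the test. It also says: "Reduction in number of UUI episodes from baseline will be summarized for each follow up visit". It does not say whether that summary is a mean or a median, and neither document plans a confidence interval.

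**The concern.** Hypothesis and sample size concern a mean, but the test behind the p-value is settled only after the data are seen. Shapiro-Wilk sends skewed data to Wilcoxon, which is where Wilcoxon stops being a test of the mean. The design gives some reason to doubt symmetry: follow-up counts cannot fall below zero, and protocol Section 10 requires at least 3 UUI episodes on the baseline diary. If changes are skewed, the rule need not hold 5% for the null as written, its power can fall below the planned 90%, and a reported mean reduction could stand beside a p-value that does not test it. This is the single primary test of a single-arm study whose aim is a significant reduction, so the question deserves a check.

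**Working it through.** **1. The plan's own figure.** Inputs from SAP Section 6: reduction 0.75, SD 2.2, two-sided alpha 0.05, power 90%. Normal approximation: (2.2 × (1.960 + 1.282) / 0.75)² = 9.51² = 90.4, so 91. The exact one-sample t-test (noncentral t, noncentrality 0.75/2.2 × √93 = 3.29) needs 93 and has 90.2% power. The plan's figure reproduces. At the cited reduction of 1.0 per day, power with 93 is 99.1%.

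**2. The rule under assumed continuous shapes.** The documents give no shape, so these are assumptions: n = 93, SD 2.2, Shapiro-Wilk p < 0.05 leads to Wilcoxon and otherwise the t-test, shifted gamma for the skewed cases, 20,000 runs each.

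| True mean reduction | Shape of changes | Rule rejects | t-test rejects |
|---|---|---|---|
| 0 | normal | 5.1% | 5.0% |
| 0 | symmetric, heavy-tailed (Laplace) | 4.9% | 5.0% |
| 0 | skewness 1 | 12.7% | 5.5% |
| 0 | skewness 2 | 35.7% | 5.9% |
| 0.75 | normal | 90.1% | 90.2% |
| 0.75 | skewness 1, few large improvers | 73.5% | 92.8% |
| 0.75 | skewness 2, few large improvers | 51.5% | 95.3% |
| 0.75 | skewness 1, few large worseners | 96.1% | 88.0% |
| 0.75 | skewness 2, few large worseners | 99.0% | 85.9% |

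Asymmetry is what matters; non-normality alone does no harm. Direction matters too. At zero mean change with a few large improvers, almost none of the excess rejections are reductions (0.4% of trials at skewness 1), so they cannot support the objective. With a few large worseners nearly all are reductions. At the cited 1.0 per day with a few large improvers, the rule keeps 94% power even at skewness 2.

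**3. The rule on diary counts.** Shifted gammas are not diary data. A closer model draws 3-day Poisson counts around a gamma-distributed personal rate (assumed mean 1.5 to 3 per day, gamma shape 1.5 or 3), with n = 93.

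- Inert treatment, no entry floor: the rule rejects in 4.7% to 6.1% of trials and the t-test in 4.5% to 6.0%, although Shapiro-Wilk rejects in 40% to 82%. Baseline and follow-up are exchangeable here, so changes are symmetric and Wilcoxon is valid.
- Inert treatment, entry floor of 3 UUI episodes: both are inflated by regression to the mean, the t-test to 8%–46% and the rule to 8%–53%. Fixing the t-test leaves most of this in place.
- Floor of 3, same proportional response in everyone, mean change 0: rule 5% to 6%, t-test 5%.
- Floor of 3, responder-type benefit: rule 89% to 100%, t-test 92% to 100%. The worst pair is 88.8% against 92.3%, a loss of 3.5 points.
- Floor of 3, log-normal individual response (log-SD 0.4 to 0.6), mean change 0: rule 9% to 25%, nearly all reductions; t-test 4% to 6%. The typical subject does improve here, and a minority who worsen a lot pull the mean back to zero.

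**4. What fixing one test would cost.** In four log-normal scenarios near the planned values (mean 0.70 to 0.79, SD 1.96 to 2.48), the rule has over 99% power and the t-test 94.6%, 87.6%, 85.4% and 83.5%. With symmetric heavy tails (t with 4 df) at 0.75, it is 96% against 90%. Naming Wilcoxon instead would mean restating the hypothesis and the sample size: 93 × π/3 = 97.4, so 98 for normal changes, and 93/0.864 = 107.6, so 108 at worst under a symmetric shift. Attrition of 20% from 120 leaves 96.

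**5. Secondary objectives.** The same rule applies. For voids, 0.63 × 93 gives about 58 subjects. At a reduction of 2.0 with a few large improvers (skewness 1 to 2), the rule has 90% to 93% power and the t-test 98% to 99%. At the cited 2.4 both have 99% or more.

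**The case for a change.** The best case for a change is that the parameter behind the headline p-value should be known before the data are seen, and that naming the t-test needs only wording: n stays 93 and no data are added. Symmetry is neither assumed nor checked, and no sensitivity analysis reports the other test. In the four log-normal scenarios near plan, the rule is significant while the t-test is not in 5% to 16% of trials.

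The logical point stands: after a switch to Wilcoxon, the p-value is not strictly a test of equal means. It also stands that the Shapiro-Wilk cut-off is not spelled out, although an analyst would take 0.05 from SAP 7.2, and that leaves no discretion.

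The practical case is weaker. The largest figures need strong skewness that the documents do not show, and a zero mean under such skewness requires some subjects' worsening to cancel others' improvement exactly. The disagreement with the t-test sets the plan against an analysis it does not contain, since no confidence interval for the mean is planned. The diary models also rest on a floor of 3 UUI episodes from protocol Section 10, whereas inclusion criterion 2 counts urgency episodes, so even that input is not settled in the documents.

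**Conclusion.** No change is called for. The rule is pre-specified in both documents, is applied mechanically and follows a common convention. Its mismatch with the mean hypothesis matters only if within-subject changes are clearly asymmetric. The documents do not say whether they are. In diary-count models with uniform or responder-type response, the rule and the t-test differ by about 4 points at most. With very variable response, the rule rejects a zero mean too often (9% to 25%), but it also has more power than the t-test near the planned effect. Moving to a fixed t-test would buy a p-value for exactly the stated mean at the price of power in plausible shapes. Moving to Wilcoxon alone would mean restating the hypothesis and sample size. Mean against signed-rank for skewed counts is a fair trade-off, and the plan's side of it is defensible.

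This rests on the assumed diary models, a Shapiro-Wilk cut-off of 0.05 and 93 evaluable subjects. Evidence of strong skewness together with a true reduction nearer 0.75 than 1.0 per day would weaken it.
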